Essure HyCoSy Ultrasound Grant Application

Can Contrast Infused Sonography Using Air Bubbles Replace Hysterosalpingogram as the Diagnostic Evaluation of Fallopian Tube Patency Following Hysteroscopic Sterilization Using Essure™?

Revision 2; Version date: 04/19/2016

[name] M.D., MMM [name], and [name]

NCT02628873

Hypothesis:

We hypothesize that performing saline infused sonography (SIS) with directed air bubbles for hysterosalpingo-contrast sonography (HyCoSy) is at least as equivalent or superior in evaluation of fallopian tube patency following hysteroscopic Essure™ tubal sterilization in those undergoing X-ray hysterosalpingography (HSG). We also hypothesize that performing HyCoSy with air bubbles is more cost-effective and less painful than HSG.

Objectives:

Currently, in the USA, Essure is approved by the Food and Drug Administration (FDA) for hysteroscopic sterilization (1). The effectiveness of permanent sterilization is 99.8%, with successful bilateral placement rate for each delivery system approximately 96.5% (1,2). Current FDA labeling for Essure requires an HSG 3 months after placement to confirm the proper coil position and tubal occlusion (1). However, HSG is not the ideal confirmatory test given the following inherent issues (3-5):

1. Exposure to ionizing radiation
2. Cost
3. Patient discomfort
4. Inconvenience
5. Poor inter-observer reproducibility
6. Variability in the technique
7. Tubal spasm potentially creating the false impression of proximal tubal occlusion

In fact, 30% of unintended pregnancies after hysteroscopic tubal occlusion placement have been attributed to misinterpretation of the HSG (6). Thus, our primary objective is to determine if HyCoSy with air bubbles is equivalent to HSG in the diagnosis of tubal patency in patients undergoing hysteroscopic sterilization using Essure™. Secondary objectives include 1) Pain assessment of each

procedure and 2) Cost analysis. To address these objectives we propose the following specific aims:

Primary Specific Aims:

1. To demonstrate an equivalent or superior evaluation of fallopian patency by HyCoSy using air-bubbles in comparison to HSG.

Secondary Specific Aims:

1. To compare pain scores in those undergoing SIS/HyCoSy to HSG in order to assess overall tolerability of SIS/HyCoSy.
2. To compare assessment of the uterine cavity using SIS air-bubble contrast using SIS-catheter in comparison to HSG.

Background and Significance:

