The advantages of HyCoSy revolve around its applicability in the office, its cost effectiveness and the avoidance of radiation exposure. Although shown to be a practical procedure with investigations yielding high accuracy results for both tubal patency and tubal occlusion, as mentioned previously, studies are still needed to evaluate this subject matter further. Minimal data exist directly comparing HSG versus HyCoSy with air bubble contrast media as the confirmatory test for post hysteroscopic tubal occlusion. We propose to determine the predictive value and possible overall superiority of HyCoSy to HSG from a time effective and pain scale model.

Experimental Design:

Thirty-six women who are undergoing post-Essure tubal occlusion evaluation will be invited to participate in this study. Subjects will be recruited and screened from the practice of Wright State OB-GYN Physicians.

Inclusion Criteria

1. Documentation of normal PAP smear within one year prior to subject enrollment in study.
2. Written consent to this study must be given voluntarily.
3. Need for evaluation of tubal status for post-Essure tubal occlusion.
4. Negative urine pregnancy test.

Exclusion Criteria

1. Any prior endometrial ablation procedures or plans to undergo endometrial ablation procedures prior to the Essure confirmation test.
2. History of unresolved dysfunctional uterine bleeding (DUB).
3. History of a hysterectomy.
4. Current urogenital disease.
5. History of allergic response to IVP dye (exclusion for HSG).
6. Abnormal pap smear.
7. Positive urine pregnancy test.

Procedure

As part of their post-Essure Tubal occlusion assessment, both air bubble HyCoSy and HSG will be performed at the same visit. Patients will undergo air bubble HyCoSy first, performed in the office setting, followed by HSG, which will be performed in the radiologic suite Miami Valley Hospital. A Likert Pain Scale will be completed prior to testing and at completion of the study for each procedure (See below).

1. Saline Infused Sonography (SIS):

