This will be a randomized prospective clinical trial, where patients will be randomly allocated to the Air Contrast HyCoSy or HSG initially followed by the other test with at least 1 hour between procedures. The primary outcome of interest is the agreement between the HSG and air-bubble HyCoSy in evaluating tubal patency. For this purpose the HSG will indicate either tubal patency or non-patency and will be considered as the gold standard, and the air-bubble HyCoSy will indicate either patency, non-patency, or inconclusive and compared to the gold standard HSG. Agreement between the evaluations will be measured using the kappa (κ) statistic. To detect a difference in kappa (a correlation) as small as 95% vs 99% you will need 36 with a 20% non-compliance rate. This means that you will be able to detect a difference as small as 95-99 OR anything larger. This translates into the assumption that even a 95% kappa is acceptable enough to call the methods 'the same.'

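### The sample-size paragraph turns a detectable kappa difference (0.95 versus 0.99) into an acceptance limit, and about 29 evaluable women cannot support a claim about 0.95 in either direction

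*Combined protocol and SAP*

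**What the plan says.** The Objectives section of the combined protocol and SAP sets out to "determine if HyCoSy with air bubbles is equivalent to HSG in the diagnosis of tubal patency". The Statistics section takes HSG as the reference and states: "Agreement between the evaluations will be measured using the kappa (κ) statistic".

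The sample size follows in three sentences. The first gives the contrast, "To detect a difference in kappa (a correlation) as small as 95% vs 99" per cent, and the number: "you will need 36 with a 20% non-compliance rate". The second restates it: "you will be able to detect a difference as small as 95-99 OR anything larger". The third draws the conclusion that "even a 95% kappa is acceptable enough" for the two tests to count as the same. Experimental Design gives the same total of 36 women.

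The section does not say which of 0.95 and 0.99 is the null. It gives no alpha, sidedness, power, expected patency rate or decision rule, and names no kappa below 0.95.

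**The concern.** The last sentence treats the smallest difference the study can detect as though it were the largest difference that is tolerable. These are different quantities. The first depends on sample size and error rates; the second is a judgement about how much disagreement with HSG would matter.

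The trial asks whether HyCoSy could replace HSG as the confirmatory test. That calls for a contrast between agreement too poor to accept and agreement good enough to accept, with a stated chance of wrongly accepting the former. As written, the paragraph gives neither that chance nor the chance of correctly accepting a true kappa of 0.95. A high observed kappa could then be reported as equivalence with no stated error control.

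**Working it through.** **Inputs from the plan.** Kappa values 0.95 and 0.99; 36 women including 20% non-compliance, so 36 × 0.8 = 28.8, about 29 evaluable.

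**Assumptions, because the plan is silent.** One-sided alpha 0.05; one binary result per woman; the same patency rate p on both tests; p from 3.5% to 50%. The low end is suggested by the 96.5% bilateral placement rate in Objectives, which is not itself a patency rate.

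**The stated 36.** It cannot be reproduced uniquely without alpha and power. The plan calls kappa a correlation, so Fisher's z was tried: atanh(0.99) − atanh(0.95) = 2.6467 − 1.8318 = 0.8149.
- One correlation, two-sided 5%, 80% power: ((1.960 + 0.842)/0.8149)² + 3 = 14.8, so 15, or 19 after dividing by 0.8. At 90% power: 19, or 24.
- Two independent correlations, per group: 2 × ((1.960 + 0.842)/0.8149)² + 3 = 26.6, so 27, or 34. At one-sided 5% and 90% power: 29, or 37.

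The two-sample version comes near 36, but this design has one paired sample and one kappa. A one-sample kappa-variance formula, with null 0.95, true value 0.99, one-sided 5% and 80% power, needs 250 evaluable (313 enrolled) at 50% patency and 2353 enrolled at 3.5%. The most favourable kappa formula tried (goodness-of-fit, null 0.99, 50% patency, one-sided 5%, 80% power) needs 97 enrolled.

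**Exact calculation.** Chance agreement is p² + (1−p)², so the probability that the two tests disagree in a woman is d = (1−κ) × 2p(1−p). The number of discordant women is binomial(29, d).

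*Reading A: 0.99 is the null.* Reject when discordances are too many.

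*Reading B: 0.95 is the lower margin and 0.99 the expected value.* Reject when discordances are few enough. The most favourable result is none, with probability (1−d)²⁹ under κ = 0.95. This must be at most 0.05 for any rejection to be possible.

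| Patency p | d at κ = 0.95 | Reading B: P(no discordance) at 0.95 | Reading A: power at 0.95 |
|---|---|---|---|
| 3.5% | 0.0034 | 0.91 | 9% (reject at ≥1) |
| 10% | 0.009 | 0.77 | 3% (reject at ≥2) |
| 20% | 0.016 | 0.63 | 8% (≥2) |
| 30% | 0.021 | 0.54 | 12% (≥2) |
| 50% | 0.025 | 0.48 | 16% (≥2) |

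Under Reading B no rejection region exists at any of these rates. With all 36 women evaluable, the probability still runs from 0.89 (3.5%) to 0.40 (50%). In the best case, 50% patency, perfect agreement first rules out 0.95 at ln(0.05)/ln(0.975) = 118.3, so 119 evaluable women.

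**What 29 women can do.** Take the null as κ ≤ k0 and the truth as 0.95. Reject if discordances ≤ c, with c the largest value for which P(X ≤ c) ≤ 0.05 at k0.

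| Patency | k0 = 0.40 | k0 = 0.60 | k0 = 0.80 |
|---|---|---|---|
| 5% | 0% | 0% | 0% |
| 10% | 77% (c = 0) | 0% | 0% |
| 20% | 92% (c = 1) | 63% (c = 0) | 0% |
| 30% | over 99% (c = 3) | 88% (c = 1) | 0% |
| 50% | over 99% (c = 4) | 84% (c = 1) | 48% (c = 0) |

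A 0% entry means that even perfect agreement is not significant. For example, k0 = 0.40 at 5% patency gives d = 0.6 × 0.095 = 0.057 and 0.943²⁹ = 0.18. The dip from 88% to 84% at k0 = 0.60 comes from discreteness: at 50% patency, P(X ≤ 2) = 0.052 just misses.

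**The case against.** The strongest defence is Reading B. Calling even 0.95 acceptable naturally marks it as the lowest tolerable value, with 0.99 as the expected one. Sizing an equivalence-type study on margin versus expected value is standard, and equivalence is the stated aim. That defence stands as far as it goes.

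A reader might therefore infer too much from the paragraph in three ways:
- **That it contradicts itself on every reading.** The wording does not support this, because Reading B is coherent. A test at the margin that fails about 95% of the time when the true kappa equals the margin shows only its 5% type I error.
- **That no sample size could repair it.** Under Reading B, enough women and a lower-limit rule would repair it.
- **That the plan treats no kappa as unacceptable.** The word even implies that lower values are worse, and the second sentence extends detection to larger differences. But no such value is named or tied to a decision.

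It is also fair to say that the plan specifies no hypothesis test, so the Reading A power describes a test that the reader has to supply. And k0 values of 0.40, 0.60 and 0.80 have no source in the documents. The percentage agreements cited in Background are raw agreement, not kappa, and do not supply one.

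None of this rescues the stated claim. Reading B is not written down, and 36 women cannot deliver it.

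**Conclusion.** The step from detecting 0.95 versus 0.99 to accepting 0.95 as sameness is unsupported. With 0.99 as the null, the test and the conclusion point in opposite directions, and power at 0.95 is about 3% to 16% at 10% to 50% patency. With 0.95 as the margin the contrast is sound, but the stated size can never establish it at any patency rate examined.

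The second result does not depend on power conventions: the best possible data are not significant at one-sided 5%. The figures do rest on 29 evaluable women, one result per woman and equal, known patency rates. They ignore the inconclusive HyCoSy category that the plan allows, and any analysis by tube. Alpha, patency and k0 are assumptions throughout. Whether 36 came from an arithmetic slip cannot be judged, since its inputs are not given.

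**What to change.** Replace the last three sentences of Statistics with one hypothesis pair and a decision rule:
- **Null:** kappa at or below k0, the highest agreement that the investigators would call unacceptable, justified and fixed before data are seen.
- **Alternative:** kappa = 0.95, the level that the plan already calls acceptable.
- **Success:** the one-sided 95% lower confidence limit for kappa exceeds k0. Name the interval method. A simple large-sample interval has zero width when agreement is perfect, so it will not do here.
- **Power:** state what about 29 evaluable women give over a range of patency rates that includes low values, and how inconclusive HyCoSy results count.

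Delete the claim that 36 women detect 0.95 versus 0.99. If the investigators prefer to keep 0.95 as the margin, they should state that 36 women cannot establish it.

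The cost is one paragraph and a short recalculation. No more patients are requested. The downside is that the stated detectable contrast becomes clearly less favourable, and at low patency the plan may have to say that no useful k0 can be ruled out.
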